5.3.14. MADRS-6

5.3.14.1. Definition

MADRS-6 is the depression subscale of the full MADRS, including the following 6 items: Apparent Sadness, Reported Sadness, Inner tension, Lassitude, Inability to feel, Pessimistic thoughts.

A total score (0 to 36) is calculated by adding the scores of all 6 items. Higher scores represent a more severe condition. Imputation of the total score will be performed only when 1 item score is missing. If 2 or more items are missing, the total score will be left missing. The total score will be imputed by calculating the sum of the scores of the non-missing items and multiplying it by the ratio of the maximum possible number of items (i.e., 6) to the number of non-missing items (i.e., 5).

The MADRS-6 change from baseline at Week 24 is calculated as (MADRS-6 total score at Week 24 – Baseline MADRS-6 total score). Negative changes in MADRS-6 total score indicate improvement.

5.3.14.2. Analysis Methods

Descriptive statistics of the actual values on Baseline, Week 2, Week 4, Week 6, Week 12, Week 18, Week 24 and at follow-up and the change from baseline to each postbaseline time point will be presented for MADRS-6 total score by treatment group.

The change from baseline over time in MADRS-6 total score will be analyzed using the same MMRM as described in Section 5.3.1.2, with the continuous covariate “baseline MADRS total score” changed to “baseline MADRS-6 total score”.

As a sensitivity analysis, the change in MADRS-6 total score from baseline to each postbaseline time point will be analyzed using an ANCOVA model, using LOCF data. The derivation of the LOCF values is described in Section 5.3.1.2. The ANCOVA model will include factors for treatment, baseline insomnia status (present/absent), and baseline MADRS-6 total score as a continuous covariate. A 80% CI for the difference in LS Means and p-value will be calculated based on the contrast test statistic.

5.4. Exploratory Efficacy Endpoints

5.4.1. Consensus Sleep Diary – Morning Administration (CSD-M)

5.4.1.1. Definition

An exploratory efficacy endpoint is the change from baseline in subjective sleep parameters as measured by the CSD-M after the first 6 weeks of treatment and after 3 to 6 months of treatment. Subjects will be asked to provide answers to questions to determine their subjective experience of sleep by recording their answers in a daily sleep diary (CSD-M). The CSD-M is the only sleep diary developed with rigorous methodology for patient reported outcome development, including employing user/focus group feedback and expert feedback to establish construct validity. It has undergone psychometric testing and its content validity has been confirmed by patient focus groups. The parameters recorded include:

- self-reported sleep onset latency (sSOL)
- subjective Total Sleep Time (sTST)
- subjective Wake After Sleep Onset (sWASO)
- subjective number of nighttime awakenings (s-nNAW)
- subjective quality of sleep (sQUAL)
- subjective refreshed feeling on waking (sFRESH)

Subjects will complete the CSD-M at home after their normal morning routine and preferably within an hour of waking for the day. The CSD-M will be completed for 3 mornings leading up to and including the targeted study visit on Study Day 1, Week 6, Week 12, Week 18, and Week 24.

The definitions and computations for deriving the subjective sleep parameters of sSOL, sWASO, sTST, and s-nNAW are shown in Table 5.

Table 5: Calculation of Subjective Sleep Parameters

Parameter	Definition	Computation
sSOL (minutes)	How many minutes it takes to fall asleep, starting from the moment of intention to fall asleep	Derived from CSD-M, Question 3: “How long did it take you to fall asleep?” with the following instructions: “Beginning at the time you wrote in question 2 (i.e., ‘What time did you try to go to sleep?’), how long did it take you to fall asleep.”
sWASO (minutes)	Total amount of time awake during the night, excluding sSOL (how many minutes it takes to fall asleep) and amount of awake time between the final awakening and the time of getting out of bed	Derived from CSD-M, Question 5: “In total, how long did these awakenings last?” with the following instructions: “What was the total time you were awake between the time you first fell asleep and your final awakening.”
sTST (minutes)	Actual time slept	Derived from CSD-M, Question 8: “In total, how long did you sleep?” with the following instructions: “This should just be your best estimate, based on when you went to bed and woke up, how long it took you to fall asleep, and how long you were awake. You do not need to calculate this by adding and subtracting; just give your best estimate.”
s-nNAW (number of times)	Number of awakenings, excluding the final awakening before the final arising	Derived from CSD-M, Question 4: “How many times did you wake up, not counting your final awakening?” with the following instructions: “How many times did you wake up between the time you first fell asleep and your final awakening?”

Source: Buysse et al, 2006.^[1]

For sSOL, sTST, sWASO, s-nNAW, the average of up to 7 morning measurements will be used as the measurement for that time point. If only one measurement is provided, it will be used as the average.

The parameter sQUAL is derived from CSD-M, Question 9: “How would you rate the quality of your sleep?”, with the instructions “Sleep Quality is your sense of whether your sleep was good or poor.” There are 5 possible responses: “Very poor”, “Poor”, “Fair”, “Good”, and “Very good”.

The parameter sFRESH is derived from CSD-M, Question 10: “How rested or refreshed did you feel when you woke-up for the day?”, with the instructions “This refers to how you felt after you were done sleeping for the night, during the first few minutes that you were awake.” There are 5 possible responses: “Not at all rested”, “Slightly rested”, “Somewhat rested”, “Well-rested”, and “Very well-rested”.

For sQUAL and sFRESH, in order to create a single “average” response, the categorical responses will be mapped to a 0-4 scale and an average will be calculated. This average will also be mapped back to the closest categorical response. For example, if sQUAL is answered “Very poor”, “Poor” and “Good”, these would be mapped to scores of 0, 1, and 3, respectively, and the average would be calculated as 1.33. As this is closest to 1, the average response would be “Poor”.

5.4.1.2. Analysis Methods

Descriptive statistics of the actual values on Average predose, Week 6 (Average), Week 12 (Average), Week 18 (Average), and Week 24 (Average) and the change from Average predose to each postbaseline time point will be presented by treatment group for sSOL, sTST, sWASO, and s-nNAW.

The change from Average predose for sSOL, sTST, sWASO, s-nNAW, sFRESH and sQUAL will be analyzed using the same MMRM as described in Section 5.3.1.2 for MADRS total score, with the continuous covariate “baseline MADRS total score” changed to the corresponding baseline score for sSOL, sTST, sWASO, s-nNAW, sFRESH, and sQUAL respectively. For sFRESH and sQUAL, an additional analysis of the change from average predose to each postbaseline time point will be performed using an ANCOVA model on the ranks of the change in score with treatment and baseline insomnia status as factors, and unranked average predose score as a covariate.

In addition, for sFRESH and sQUAL, a frequency distribution of the average categorical response will be provided for Average predose, Week 6 (Average), Week 12 (Average), Week 18 (Average), and Week 24 (Average). In addition, the shift in average categorical response from Average predose to each of the postbaseline time points will be presented.

Descriptive statistics of the actual values on Average predose, Week 6 (Average), Week 12 (Average), Week 18 (Average), and Week 24 (Average) and the change from Average predose to each postbaseline time point will be presented by treatment group for average number of naps, the average total duration of naps (in minutes), the average number of drinks containing alcohol, and the average number of caffeinated drinks.

5.4.2. MADRS-WOSI

5.4.2.1. Definition

MADRS-WOSI is defined as the full MADRS with the item Reduced Sleep excluded.

A total score (0 to 54) is calculated by adding the scores of all 9 items. Higher scores represent a more severe condition. Imputation of the total score will be performed only when 1 item score is missing. If 2 or more items are missing, the total score will be left missing. The total score will be imputed by calculating the sum of the scores of the non-missing items and multiplying it by the ratio of the maximum possible number of items (i.e., 9) to the number of non-missing items (i.e., 8).

The MADRS-WOSI change from baseline at Week 24 is calculated as (MADRS-WOSI total score at Week 24 – Baseline MADRS-WOSI total score). Negative changes in MADRS-WOSI total score indicate improvement.

5.4.2.2. Analysis Methods

Descriptive statistics of the actual values on Baseline, Week 2, Week 4, Week 6, Week 12, Week 18, Week 24 and at follow-up and the change from baseline to each postbaseline time point will be presented for MADRS-WOSI total score by treatment group.

The change from baseline over time in MADRS- WOSI total score will be analyzed using the same MMRM as described in Section 5.3.1.2, with the continuous covariate “baseline MADRS total score” changed to “baseline MADRS- WOSI total score”.

6. SAFETY

All safety analyses will be based on the safety analysis set based on actual treatment received, unless otherwise specified.

6.1. Adverse Events

The verbatim terms used in the CRF by investigators to identify AEs will be coded using the Medical Dictionary for Regulatory Activities (MedDRA). Any AE occurring at or after the initial administration of study agent through the day of last dose plus 2 days is considered to be treatment-emergent. If the AE occurs on the day of the initial administration of study agent, and either AE time or time of administration are missing, then the AE will be assumed to be treatment-emergent. If the event date is recorded as partial or completely missing, then the event will be considered to be treatment-emergent unless it is known to be prior to the first administration of study agent based on partial onset date or resolution date.

All reported treatment-emergent adverse events (TEAEs) will be included in the analysis. For each TEAE, the number and percentage of subjects who experience at least 1 occurrence of the given event will be summarized by system organ class, preferred term, and treatment group (and overall).

Summary tables will be provided for:

- TEAEs
- TEAEs occurring in $\geq 5\%$ of subjects in either treatment group
- Treatment-emergent serious AEs (SAEs)
- TEAEs leading to discontinuation of study agent
- TEAEs by severity
- TEAEs by most recent treatment dose
- AEs by relationship to study agent
- AEs leading to dose interruption (overall and by most recent treatment dose)
- AEs leading to dose modification (increase or decrease)

For the summaries of TEAEs by severity/relationship to study drug, the observation with the most severe occurrence/closest relationship to study agent will be chosen if there is more than one incident of the same TEAE for the subject.

In addition, a summary table will be generated showing the number and percentage of subjects who experience at least 1 occurrence of a given TEAE by system organ class, preferred term, lowest level term, and treatment group.

A summary of all somnolence-related TEAEs (MedDRA preferred terms: somnolence, hypersomnia, and sedation; regardless of start time) will be presented.

Adverse events of special interest are cataplexy, sleep paralysis, and complex, sleep-related behaviors (parasomnias). Subjects with TEAEs of special interest will be presented separately, by preferred term and treatment group. The AEs to be included in the summary of TEAEs of special interest are marked as such on the AE CRF.

A summary table of non-TEAEs occurring on or after the date of last dose of study drug plus 3 days until the overall reference end date for the study will also be provided.

In addition to the summary tables, listings will be provided for subjects who:

- Died
- Had SAEs
- Had AEs leading to discontinuation of study agent
- Had somnolence-related TEAEs
- Had suicide-related TEAEs
- Had TEAEs of special interest

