### ***Adverse Events of Special Interest***

The following AEs are considered to be of special interest in this study:

- Cataplexy (sudden, transient episode of muscle weakness accompanied by conscious awareness)
- Sleep paralysis (the experience of not being able to move, react, or speak when falling asleep/awakening)
- Complex, sleep-related behaviors/parasomnias such as confusional arousals, somnambulism (sleep walking), sleep terrors, bruxism (teeth grinding), sleep sex, sleep-related eating disorder, sleep behavior disorder, and catathrenia (REM-associated end-inspiratory apnea/breath holding)

Investigators are instructed to inquire about the occurrence of such events during the collection of AEs at each visit. When reported, the investigator will be required to complete a detailed summary of the event and its clinical course utilizing the AE of special interest narrative form as soon as information on the outcome (recovered, resolving, or ongoing) is available. In addition, the AE should be marked as an AE of special interest in the CRF. Note: If the event meets the seriousness criteria (see Section 12.1.1), the Serious Adverse Events Form must also be completed according to the serious adverse events reporting timeline described in Section 12.3.2, ie, within 24 hours of having become aware of the event, even if all details are not available.

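### SAP 6.1 selects adverse events of special interest by the investigator's CRF mark alone, so a matching coded event without a mark would be missing from that summary

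*SAP*

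**What the plan says.** Protocol 9.7 (Adverse Events of Special Interest) names three groups: cataplexy, sleep paralysis, and parasomnias. The third is an open list of examples that begins "Complex, sleep-related behaviors/parasomnias such as confusional arousals, somnambulism (sleep walking), sleep terrors, bruxism (teeth grinding" and goes on to four more. Sites are told to look for these events: "Investigators are instructed to inquire about the occurrence of such events during the collection of AEs at each visit". When one is reported, the site completes a narrative form, and "In addition, the AE should be marked as an AE of special interest in the CRF".

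SAP 6.1 repeats the three concepts and says how they are shown: "Subjects with TEAEs of special interest will be presented separately, by preferred term and treatment group". It then gives the selection rule: "The AEs to be included in the summary of TEAEs of special interest are marked as such on the AE CRF". It provides no preferred-term list, no standardised MedDRA query and no step that compares marked events with coded events. The listing of subjects with AESIs, later in the same section, has no definition of its own.

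For a neighbouring group of events the same section works from coded terms: "A summary of all somnolence-related TEAEs (MedDRA preferred terms: somnolence, hypersomnia, and sedation; regardless of start time) will be presented".

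**The concern.** The protocol treats the mark as a reporting instruction that follows from the concept definition. The SAP makes it the only condition for entering the summary. A programmer who follows SAP 6.1 literally filters on the mark, and an unmarked event that matches the concept does not enter.

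Some concepts are easy to leave unmarked. The parasomnia list is open-ended, and a site may not think of bruxism as an event of special interest. Attachment 2 of the protocol also lists abnormal sleep as an anticipated consequence of the disease, which offers another label for borderline reports.

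The output at stake is a stated one. The proportion of events of special interest is among the secondary safety endpoints in protocol 2.1, and protocol 3.2 explains why these events are followed in an orexin antagonist. A reader of the AESI table alone could not tell that an unmarked event had been left out.

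**Working it through.** The plan states no figure on this point, so the check is mainly a comparison of texts.

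**Step 1: follow one event through the plan.** Take a treatment-emergent event coded to sleep paralysis, with the CRF mark missing.

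| Output | Rule in SAP 6.1 | Is the event included? |
|---|---|---|
| All treatment-emergent events by preferred term | "All reported treatment-emergent adverse events (TEAEs) will be included in the analysis" | Yes |
| Table with lowest level term | "by system organ class, preferred term, lowest level term, and treatment group" | Yes |
| Events in at least 5% of either group | 0.05 × 50 = 2.5, so at least 3 subjects with the same term | Only if 3 or more subjects have it |
| AESI summary | Mark on the CRF | No |
| AESI listing | No separate rule, so presumably the mark | Presumably no |

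**Step 2: can the general tables replace the AESI summary?** In part. They show each preferred term by arm. They do not give a proportion of subjects with any parasomnia. Rows for different parasomnia terms cannot simply be added, because one subject may appear in several rows.

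**Step 3: how small are the counts?** The planned size is 50 per arm (SAP 1.4). The only documentary anchor for frequency is 3 sleep paralysis cases to date (protocol 3.2) among 271 subjects who received the drug (protocol 1.1.2): 3/271 = 1.1%, or 50 × 3/271 = 0.55 expected cases per arm. This anchor is weak. Earlier exposure was much shorter than 24 weeks, and the other AESIs are not counted in it.

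**Step 4: illustration only.** Let p be the true proportion of subjects in an arm with an AESI and s the chance that such a subject's event is marked. The documents give neither. With n = 50:

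- expected subjects in the AESI table = 50 × p × s
- chance of at least one subject in the table = 1 − (1 − p × s)^50

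| p (assumed) | s (assumed) | Expected in table | Chance of at least one |
|---|---|---|---|
| 2% | 100% | 1.0 | 0.64 |
| 2% | 90% | 0.9 | 0.60 |
| 2% | 75% | 0.75 | 0.53 |
| 2% | 50% | 0.5 | 0.40 |
| 4% | 100% | 2.0 | 0.87 |
| 4% | 90% | 1.8 | 0.84 |
| 4% | 75% | 1.5 | 0.78 |
| 4% | 50% | 1.0 | 0.64 |

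The 100% rows show the table with complete capture. The illustration shows only that counts are small enough for a single unmarked event to alter the table. It does not estimate how many will be unmarked.

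**The case against.** The case against is substantial.

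- **No data are lost.** Every treatment-emergent event is tabulated by preferred term and arm, marked or not. The AESI summary is also by preferred term, so with about 50 subjects per arm a careful reader could compare the two. A reader might infer that unmarked events vanish from the trial's results; they do not. What stands is that the combined AESI proportion cannot be rebuilt from those tables.
- **The mark applies the concept.** It is made by an investigator who has been told to ask about these events at each visit and to write a narrative. Protocol 17.5 and 17.6 add CRF completion guidelines, sponsor review for completeness, and queries. All of this lowers the chance of a missing mark. None of it changes the selection rule.
- **Somnolence is not a strict parallel.** The documents describe no CRF mark for somnolence, so a term list is needed there. The contrast shows that a term-based rule is workable in this SAP, not that the SAP contradicts itself.
- **Early events.** Because the amendment log places the marking sentence in Amendment 2, a reader might infer that earlier events carry no mark. The log shows that a detailed summary on a CRF page was already required. The documents do not say whether any such event had occurred by then or how it was recorded, so the inference is speculative.
- **Importance.** A reader might take this as the trial's central safety question. Protocol 3.2 reports that animal studies suggest cataplexy may not be a liability for selective OX2R antagonists, and the AESI proportion is one of several safety assessments, with no formal test planned.

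**Conclusion.** The point holds as a gap in specification. The CRF mark is the only inclusion rule given for the AESI summary, while the protocol defines the events by concept. An unmarked event that matches would be missing from that summary and presumably from the listing, and the AESI proportion could be too low.

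No size can be derived. A reader might want a probability that an event is missed, but any such figure rests wholly on an assumed marking rate and an assumed number of events. The documents do not show that marks will be missed, and data-review procedures held outside them cannot be ruled out. The primary endpoint and the general adverse event tables are unaffected. The change is worth making because it is cheap and makes a named safety endpoint more complete.

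**What to change.** In SAP 6.1, define a treatment-emergent event of special interest as one that is either marked on the AE CRF or coded to a MedDRA preferred-term list. The list should cover the concepts in protocol 9.7 and be frozen before unblinding. Then:

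1. build the AESI summary and listing from the combined definition;
2. show in the listing whether each event entered by mark, by term or by both;
3. query events that match on only one source before database lock.

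The cost is one term list, one programmed flag and a few data queries. Keeping the CRF route means that no event identified by an investigator drops out. The downside is that a few non-specific events, for example some reports of bruxism, may be added; the source column makes these visible.

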6.2. Clinical Laboratory Tests

Descriptive statistics will be presented for thyroid-stimulating hormone (TSH) and free thyroxine (FT₄), as well as all chemistry (including the lipid panel), hematology (including hemoglobin A1c [HbA1c]), and urinalysis (pH and specific gravity) laboratory parameters at each scheduled time point. In addition, change from baseline to all postbaseline time points will be summarized for chemistry, hematology, urinalysis (pH and specific gravity), TSH, and FT₄ parameters and displayed by treatment group.

The number and percentage of subjects with treatment-emergent postbaseline markedly abnormal postbaseline values will be presented by treatment group. Clinical laboratory test values will be considered “treatment-emergent markedly abnormal” (TEMA) using the criteria defined by the sponsor listed in Attachment 4. The identification of TEMA laboratory values is based on the postbaseline value being out of range while the baseline value is either missing or within the range given in Attachment 4. If postbaseline laboratory results are above the upper limit and the baseline value is below the lower limit, then the postbaseline abnormality will also be considered TEMA. The same applies to the postbaseline value being below the lower limit with the baseline value being above the upper limit.

In addition, the number of subjects with the following shifts in chemistry laboratory values from baseline to the maximum postbaseline time point will be presented:

- Glucose:
 - from <100 mg/dL to ≥ 126 mg/dL (normal to high)
 - from <100 mg/dL to [≥ 100 mg/dL - <126 mg/dL] (normal to borderline high)
 - from [≥ 100 mg/dL - <126 mg/dL] to ≥ 126 mg/dL (borderline high to high)
- Triglycerides:
 - from <150 mg/dL to ≥ 200 mg/dL (normal to high/very high)
 - from <150 mg/dL to ≥ 500 mg/dL (normal to very high)
 - from [≥ 150 mg/dL - <200 mg/dL] to ≥ 200 mg/dL (borderline high to high/very high)
 - from [≥ 150 mg/dL - <200 mg/dL] to ≥ 500 mg/dL (borderline high to very high)
 - from [≥ 200 mg/dL - <500 mg/dL] to ≥ 500 mg/dL (high to very high)
- Total Cholesterol
 - from <200 mg/dL to ≥ 200 mg/dL (normal to borderline high/high)
 - from <200 mg/dL to ≥ 240 mg/dL (normal to high)
 - from <200 mg/dL to [≥ 200 mg/dL - <240 mg/dL] (normal to borderline high)
 - from [≥ 200 mg/dL - <240 mg/dL] to ≥ 240 mg/dL (borderline high to high)
- HDL Cholesterol: from ≥ 40 mg/dL to <40 mg/dL (normal to low).

The following conversion rules will be used: Glucose 1 mg/dL=0.05551 mmol/L; Triglycerides 1 mg/dL=0.01129 mmol/L; Total Cholesterol, HDL Cholesterol 1 mg/dL=0.02586 mmol/L.

The incidence of subjects with treatment-emergent ALT values >3 *upper normal limit (ULN), AST > 3 *ULN, or total bilirubin >2 *ULN will be presented for the double-blind phase. Additionally, incidence of treatment-emergent hepatic toxicity (suspected Hy's Law⁴ cases) defined as (ALT values >3 *ULN or AST values > 3 *ULN) AND total bilirubin values >2 *ULN will be presented for the double-blind phase. Similar to the markedly abnormal analysis, only subjects with baseline (ALT values ≤ 3 *ULN or AST ≤ 3 *ULN) (AND baseline total bilirubin values ≤ 2 *ULN for hepatic toxicity) (or if baseline value is missing) will be eligible for these analyses.

A listing of subjects with markedly abnormal laboratory values will be provided.

